11.6 Appendix 6. Sample Storage and Destruction

Any blood biomarkers and pharmacokinetics sample collected according to the Schedule of Activities (**Section 1.3**) can be analyzed for any of the tests outlined in the protocol and for any tests necessary to minimize risks to study subjects. This includes testing to ensure analytical methods produce reliable and valid data throughout the course of the study. This can also include, but is not limited to, investigation of unexpected results, incurred sample reanalysis, and analyses for method transfer and comparability.

All samples and associated results will be coded prior to being shipped from the site for analysis or storage. Samples will be tracked using a unique identifier that is assigned to the samples for the study. Results are stored in a secure database to ensure confidentiality.

If informed consent is provided by the subject, Amgen can do additional testing on remaining samples (ie, residual and back-up) to investigate and better understand the obesity and other metabolic conditions, the dose response and/or prediction of response to AMG 133, and characterize aspects of the molecule (eg, mechanism of action/target, metabolites). Results from this analysis are to be documented and maintained, but are not necessarily reported as part of this study. Samples can be retained for up to 20 years.

Since the evaluations are not expected to benefit the subject directly or to alter the treatment course, the results of pharmacogenetic, [REDACTED] or other exploratory studies are not placed in the subject's medical record and are not to be made available to the subject, members of the family, the personal physician, or other third parties, except as specified in the informed consent.

The subject retains the right to request that the sample material be destroyed by contacting the investigator. Following the request from the subject, the investigator is to provide the sponsor with the required study and subject number so that any remaining blood samples and any other components from the cells can be located and destroyed. Samples will be destroyed once all protocol-defined procedures are completed. However, information collected from samples prior to the request for destruction, will be retained by Amgen.

The sponsor is the exclusive owner of any data, discoveries, or derivative materials from the sample materials and is responsible for the destruction of the sample(s) at the request of the subject through the investigator, at the end of the storage period, or as

appropriate (eg, the scientific rationale for experimentation with a certain sample type no longer justifies keeping the sample). If a commercial product is developed from this research project, the sponsor owns the commercial product. The subject has no commercial rights to such product and has no commercial rights to the data, information, discoveries, or derivative materials gained or produced from the sample.

See Section [11.3](#) for subject confidentiality.

11.7 Appendix 7. Hepatotoxicity Stopping Rules: Suggested Actions and Follow-up Assessments and Study Treatment Rechallenge Guidelines

Subjects with abnormal hepatic laboratory values (ie, alkaline phosphatase [ALP], aspartate aminotransferase [AST], alanine aminotransferase [ALT], total bilirubin [TBL]) and/or international normalized ratio (INR), and/or signs/symptoms of hepatitis (as described below) may meet the criteria for withholding or permanent discontinuation of Amgen investigational product or other protocol-required therapies, as specified in the *Guidance for Industry Drug-Induced Liver Injury: Premarketing Clinical Evaluation, July 2009*.

Criteria for Withholding and/or Permanent Discontinuation of Amgen Investigational Product and Other Protocol-required Therapies Due to Potential Hepatotoxicity

The following stopping and/or withholding rules apply to subjects for whom another cause of their changes in liver biomarkers (TBL, INR, and transaminases) has not been identified.

Important alternative causes for elevated AST/ALT and/or TBL values include, but are not limited to:

- Hepatobiliary tract disease
- Viral hepatitis (eg, hepatitis A/B/C/D/E, Epstein-Barr Virus, cytomegalovirus, herpes simplex virus, varicella, toxoplasmosis, and parvovirus)
- Right sided heart failure, hypotension or any cause of hypoxia to the liver causing ischemia
- Exposure to hepatotoxic agents/drugs or hepatotoxins, including herbal and dietary supplements, plants and mushrooms
- Heritable disorders causing impaired glucuronidation (eg, Gilbert's syndrome, Crigler-Najjar syndrome) and drugs that inhibit bilirubin (BIL) glucuronidation (eg, indinavir, atazanavir)
- Alpha-1 antitrypsin deficiency
- Alcoholic hepatitis
- Autoimmune hepatitis
- Wilson's disease and hemochromatosis
- Nonalcoholic fatty liver disease including steatohepatitis
- Non-hepatic causes (eg, rhabdomylosis, hemolysis)

If investigational product(s) is/are withheld, the subject is to be followed for possible drug-induced liver injury (DILI) according to recommendations in the last section of this appendix.

Rechallenge may be considered if an alternative cause for impaired liver tests (ALT, AST, ALP) and/or elevated TBL, is discovered and the laboratory abnormalities resolve to normal or baseline (see next section in this appendix).

Table 13. Conditions for Withholding and/or Permanent Discontinuation of Amgen Investigational Product and Other Protocol-required Therapies due to Potential Hepatotoxicity

Analyte	Temporary Withholding	Permanent Discontinuation
TBL	> 3x ULN at any time	> 2x ULN OR
INR	--	> 1.5x (for subjects not on anticoagulation therapy) AND
AST/ALT	> 8x ULN at any time > 5x ULN but < 8x ULN for \geq 2 weeks > 5x ULN but < 8x ULN and unable to adhere to enhanced monitoring schedule > 3x ULN with clinical signs or symptoms that are consistent with hepatitis (such as right upper quadrant pain/tenderness, fever, nausea, vomiting, and jaundice)	In the presence of no important alternative causes for elevated AST/ALT and/or TBL values > 3x ULN (when baseline was < ULN)
ALP	OR > 8x ULN at any time	--

ALP = alkaline phosphatase; ALT = alanine aminotransferase; AST = aspartate aminotransferase;
INR = international normalized ratio; TBL = total bilirubin; ULN = upper limit of normal

Permanent withholding criteria are met when AST/ALT > 3x ULN in the presence of no important alternative causes for elevated AST/ALT and/or TBL values AND 1 of the following 2 are met: TBL > 2X ULN OR > 1.5x (for subjects not on anticoagulation therapy).

Criteria for Rechallenge of Amgen Investigational Product and Other Protocol-required Therapies After Potential Hepatotoxicity

The decision to rechallenge the subject is to be discussed and agreed upon unanimously by the subject, investigator, and Amgen.

If signs or symptoms recur with rechallenge, then AMG 133 is to be permanently discontinued. Subjects who clearly meet the criteria for permanent discontinuation (as described in [Table 13](#)) are never to be rechallenged.

Drug-induced Liver Injury Reporting and Additional Assessments

Reporting

To facilitate appropriate monitoring for signals of DILI, cases of concurrent AST or ALT and TBL and/or INR elevation, according to the criteria specified in the above, require the following:

- The event is to be reported to Amgen as a serious adverse event within 24 hours of discovery or notification of the event (ie, before additional etiologic investigations have been concluded)
- The appropriate case report form (CRF) (eg, Event CRF) that captures information necessary to facilitate the evaluation of treatment-emergent liver abnormalities is to be completed and sent to Amgen

Other events of hepatotoxicity and potential DILI are to be reported as serious adverse events if they meet the criteria for a serious adverse event defined in Section 11.4.

Additional Clinical Assessments and Observation

All subjects in whom investigational product(s) or protocol-required therapies is/are withheld (either permanently or conditionally) due to potential DILI as specified in [Table 13](#) or who experience AST or ALT elevations $> 3 \times$ upper limit of normal (ULN) or 2-fold increases above baseline values for subjects with elevated values before drug are to undergo a period of “close observation” until abnormalities return to normal or to the subject’s baseline levels.

Assessments that are to be performed during this period include:

- Repeat AST, ALT, ALP, BIL (total and direct), and INR within 24 hours
- In cases of TBL $> 2 \times$ ULN or INR > 1.5 , retesting of liver tests, BIL (total and direct), and INR is to be performed every 24 hours until laboratory abnormalities improve

Testing frequency of the above laboratory tests may decrease if the abnormalities stabilize or the investigational product(s) or protocol-required therapies has/have been discontinued AND the subject is asymptomatic.

Initiate investigation of alternative causes for elevated AST or ALT and/or elevated TBL.

The following are to be considered depending on the clinical situation:

- Complete blood count with differential to assess for eosinophilia
- Serum total immunoglobulin (Ig)G, anti-nuclear antibody anti-smooth muscle antibody, and liver kidney microsomal antibody-1 to assess for autoimmune hepatitis
- Serum acetaminophen (paracetamol) levels

A more detailed history of:

- Prior and/or concurrent diseases or illness
- Exposure to environmental and/or industrial chemical agents
- Symptoms (if applicable) including right upper quadrant pain, hypersensitivity-type reactions, fatigue, nausea, vomiting and fever
- Prior and/or concurrent use of alcohol, recreational drugs and special diets
- Concomitant use of medications (including nonprescription medicines and herbal and dietary supplements), plants, and mushrooms
- Viral serologies
- Creatine phosphokinase, haptoglobin, lactate dehydrogenase and peripheral blood smear
- Appropriate liver imaging if clinically indicated
- Appropriate blood sampling for pharmacokinetic analysis if this has not already been collected
- Hepatology consult (liver biopsy may be considered in consultation with a hepatologist)

Follow the subject and the laboratory tests (ALT, AST, TBL, INR) until all laboratory abnormalities return to baseline or normal or considered stable by the investigator. The "close observation period" is to continue for a minimum of 4 weeks after discontinuation of all investigational product(s) and protocol-required therapies.

The potential DILI event and additional information such as medical history, concomitant medications and laboratory results must be captured in the corresponding CRFs.

11.8 Appendix 8. Mental Health Criteria Stopping Rules: Suggested Actions and Follow-up Assessments

Subjects with an increase in score on either the Patient Health Questionnaire 9 (PHQ-9) and/or C-SSRS assessments may meet the criteria for permanent discontinuation of Amgen investigational product or other protocol-required therapies.

Criteria for Withholding and/or Permanent Discontinuation of Amgen Investigational Product and Other Protocol-required Therapies Due to Potential Mental Health Changes

The following stopping rules apply to subjects for whom an increase in their PHQ-9 and/or C-SSRS scores have been identified.

Table 14. Conditions for Permanent Discontinuation of Amgen Investigational Product and Other Protocol-required Therapies Due to Changes in Mental Health Scores

Mental Health Assessment	Permanent Discontinuation
PHQ-9	≥ 10
C-SSRS	OR Answers yes to any items #1-5

PHQ-9 = Patient Health Questionnaire 9 ; C-SSRS = Columbia Suicide Severity Rating Scale

Reporting

To facilitate appropriate monitoring for signals of mental health changes according to the criteria specified in the above, require the following:

The event is to be reported to Amgen as a serious adverse event within 24 hours of discovery or notification of the event (ie, before additional etiologic investigations have been concluded)

The appropriate Case Report Form (CRF) (eg, Event CRF) that captures information necessary to facilitate the evaluation of treatment-emergent liver abnormalities is to be completed and sent to Amgen

Additional Clinical Assessments and Observation

All subjects in whom investigational product(s) or protocol-required therapies is/are withheld permanently due to potential mental health changes as specified in [Table 14](#) are to undergo a period of “close observation” until the subject’s care can be transferred to an appropriate mental health professional.

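### Appendix 7 gives two different permanent liver-stopping criteria for subjects whose baseline AST or ALT is at or above ULN

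*Protocol*

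**What the plan says.** Appendix 7 (Protocol Section 11.7) limits its scope first: "The following stopping and/or withholding rules apply to subjects for whom another cause of their changes in liver biomarkers" has not been found. Its list of such causes includes "Nonalcoholic fatty liver disease including steatohepatitis".

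- **Table 13, permanent column.** TBL above 2x ULN or INR above 1.5 (if not anticoagulated), together with AST/ALT "> 3x ULN (when baseline was < ULN") and no important alternative cause.
- **Sentence directly below the table.** "Permanent withholding criteria are met when AST/ALT > 3x ULN in the presence of no important alternative causes", plus one of two conditions: "TBL > 2X ULN OR > 1.5x (for subjects not on anticoagulation therapy"). It has no baseline condition. The 1.5x limit names no analyte; its position shows that INR is meant.
- **Table 13, temporary column.** Six conditions: TBL above 3x; AST/ALT above 8x; AST/ALT between 5x and 8x for at least 2 weeks; the same range when enhanced monitoring cannot be followed; AST/ALT above 3x with hepatitis-type signs or symptoms; ALP above 8x.
- **Rechallenge.** The absolute ban covers "Subjects who clearly meet the criteria for permanent discontinuation" and cites Table 13 only. Otherwise, "Rechallenge may be considered if an alternative cause for impaired liver tests" is found and the abnormalities resolve, and the decision is "to be discussed and agreed upon unanimously by the subject, investigator, and Amgen".
- **Eligibility (Section 5.2, criterion 204).** Liver values are excluded only above 1.5x ULN. An ALT above that may still be accepted after discussion with the medical monitor if AST, ALP and total bilirubin are normal.

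**The concern.** A permanent-stop rule should give one answer for a given set of results. Here it gives two whenever baseline AST/ALT is at or above ULN, because Table 13 has no permanent criterion for those subjects and the sentence beneath it does. Such subjects are expected under criterion 204: baselines from 1.0x to 1.5x ULN are simply eligible, and higher ALT is possible by exception.

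At stake is a further dose in a subject with transaminases and bilirubin raised together and no other explanation. In Part C that dose can fall due 7 days later, and chemistry is scheduled on days 8 and 15 in both cohorts, so a day 8 result can bear on the day 15 dose.

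Two other rules depend on the same criterion. The never-rechallenge rule points to the table alone. The 24-hour serious adverse event reporting duty for combined elevations points back to the criteria given earlier in the appendix, without saying whether that means the table or the sentence.

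**Working it through.** The plan states no figure to reproduce; the check is a comparison of two rules. AST/ALT, TBL and ALP are in multiples of ULN. No alternative cause is assumed throughout, and ALP is at most 8x.

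**Rules as written**

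- Table permanent = ALT > 3 and baseline < 1 and (TBL > 2 or INR > 1.5)
- Sentence = ALT > 3 and (TBL > 2 or INR > 1.5)
- Table temporary = any of the six conditions listed above

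**Applied to hypothetical subjects** (INR not above 1.5 and no symptoms unless stated)

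| Case | Baseline ALT | On-study values | Table permanent | Table temporary | Sentence |
|---|---|---|---|---|---|
| A | 1.2 | ALT 4, TBL 2.5 | no | no | yes |
| B (control) | 0.9 | ALT 4, TBL 2.5 | yes | no | yes |
| C | 1.2 | as A, with nausea consistent with hepatitis | no | yes | yes |
| D | 1.2 | ALT 4, TBL 3.5 | no | yes | yes |
| E | 1.2 | ALT 4, TBL 1.0, INR 2.0 | no | no | yes |
| F | 1.2 | ALT 6 alone | no | no | no |

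A and B differ only in baseline, so the parenthetical alone causes the split. In A none of the six temporary conditions holds: TBL is not above 3x, ALT is not above 5x, there are no symptoms, and ALP is not above 8x. The full gap is therefore baseline at or above ULN, ALT above 3x and up to 5x, TBL above 2x and up to 3x, no symptoms and no other cause. In C and D the table withholds temporarily where the sentence stops permanently. F shows that a transaminase rise alone brings no conflict.

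Case E follows from the wording but is remote. Part C schedules coagulation only at screening and day -2 (Tables 5 and 6), so an on-treatment INR would normally be drawn only once close observation had begun.

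**Who can be affected.** Part A is single-dose, so a stopping rule changes no later dose there. By December 2021, 39 Part B subjects had already received 1 to 3 doses (Section 2.2.2.4). That leaves mainly Part C, with up to 12 subjects: cohort 12 is dosed on days 1, 8, 15 and 43, and cohort 13 on days 1, 8, 15, 22, 29 and 57. Only those with a raised baseline count, and the documents do not give that fraction.

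**The case against.** The strongest reply is that both texts can be obeyed at once by stopping when either is met. Table 13 lists reasons to stop; failing to meet it is not an instruction to dose. The stricter sentence stands in plain view beneath it, and the amendment log shows that Amendment 1 added it, so it reads naturally as the operative clarification. This is a sensible reading, but the protocol does not state it. A reader might infer from the conflict that the protocol directs a further dose. It does not; the fault is that a site relying on the table alone could think one permitted.

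Safeguards outside the disputed rule also stand. Any AST/ALT above 3x ULN triggers close observation with repeat tests within 24 hours, and testing every 24 hours when TBL exceeds 2x ULN or INR exceeds 1.5. Under Section 6.2.1 the dose level review team must recommend stopping or modifying dosing for laboratory changes that put health at significant risk, and the medical monitor may suspend dosing at any time. These limit the harm but leave the mandatory rule unclear. The 24-hour reporting duty cannot be counted as a sure safeguard, since it rests on the same criteria.

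The rechallenge gap is secondary, because rechallenge normally needs an alternative cause and unanimous agreement.

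A different threshold for raised baselines would be defensible: the close-observation text already uses a 2-fold rise for them. But Table 13 states no such threshold, and the sentence contradicts leaving these subjects out.

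**Conclusion.** The point holds as a conflict between two current statements of a permanent-stop rule, and it should be fixed. It rests on the texts as they stand, on criterion 204 admitting baselines at or above ULN, and on no alternative cause being found. If fatty liver disease or another listed cause is judged responsible, neither statement applies.

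The size is small and cannot be expressed as a rate. A reader might take all later Part C doses, 6 x 3 + 6 x 5 = 48, as the number at risk. That would treat every subject as having a raised baseline and the full laboratory pattern, which the documents do not support. Counting grid combinations in which the rules differ would be no better, since within the gap they differ by construction. About 90% of subjects in cohorts 7 to 10 reported mild gastrointestinal events after the first dose (Section 4.3), so some early cases could meet the symptomatic temporary condition instead, if the symptoms were judged consistent with hepatitis.

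**What to change.** Make Table 13 and the sentence state one identical criterion. The default is to delete the baseline parenthetical from Table 13, because the sentence already imposes the stricter rule. If the sponsor wants a different threshold for raised baselines, write that tier explicitly in both places. Name INR in the sentence (INR > 1.5), and tie the never-rechallenge and 24-hour reporting rules to the single criterion.

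The cost is a few words and a short letter to sites, with no added procedures, subjects or analyses. There is one small downside. Criterion 204 sets no upper ALT limit for its exception, so a subject admitted at 2.5x ULN would reach the 3x limit after a rise of (3.0 - 2.5)/2.5 = 20%, and any further rise would meet the ALT condition. TBL above 2x ULN or INR above 1.5, and no alternative cause, would still be required. For subjects admitted with ALT above 1.5x, such a bilirubin value would be a new abnormality, since bilirubin must be normal at screening. That does not extend to baselines of 1.0x to 1.5x, where criterion 204 allows bilirubin up to 1.5x ULN.

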11.9 Appendix 9. Columbia Suicide Severity Rating Scale (C-SSRS)

Baseline Form (example shown below) is to be administered at screening visit and Since Last Visit Form at all subsequent visits by trained staff.

Figure 11-3. Sample C-SSRS Form

COLUMBIA-SUICIDE SEVERITY RATING SCALE (C-SSRS)

Baseline

Version 1/14/09

Posner, K.; Brent, D.; Lucas, C.; Gould, M.; Stanley, B.; Brown, G.; Fisher, P.; Zelazny, J.; Burke, A.; Oquendo, M.; Mann, J.

Disclaimer:

This scale is intended to be used by individuals who have received training in its administration. The questions contained in the Columbia-Suicide Severity Rating Scale are suggested probes. Ultimately, the determination of the presence of suicidal ideation or behavior depends on the judgment of the individual administering the scale.

Definitions of behavioral suicidal events in this scale are based on those used in The Columbia Suicide History Form, developed by [name] and [name], Conte Center for the Neuroscience of Mental Disorders (CCNMD), New York State Psychiatric Institute, [name]. (Oquendo M. A., Halberstam B. & Mann J. J., Risk factors for suicidal behavior: utility and limitations of research instruments. In M.B. First [Ed.] Standardized Evaluation in Clinical Practice, pp. 103 -130, 2003.)

For reprints of the C-SSRS contact [name]., New York State Psychiatric Institute, [name]; inquiries and training requirements contact [contact]

© 2008 The Research Foundation for Mental Hygiene, Inc.

SUICIDAL IDEATION		Lifetime: Time He/She Felt Most Suicidal												

Ask questions 1 and 2. If both are negative, proceed to "Suicidal Behavior" section. If the answer to question 2 is "yes", ask questions 3, 4 and 5. If the answer to question 1 and/or 2 is "yes", complete "Intensity of Ideation" section below.
														

1. Wish to be Dead Subject endorses thoughts about a wish to be dead or not alive anymore, or wish to fall asleep and not wake up. Have you wished you were dead or wished you could go to sleep and not wake up?
 
If yes, describe:
		Yes  No 												

2. Non-Specific Active Suicidal Thoughts General, non-specific thoughts of wanting to end one's life/commit suicide (e.g., "I've thought about killing myself") without thoughts of ways to kill oneself/associated methods, intent, or plan. Have you actually had any thoughts of killing yourself?
 
If yes, describe:
		Yes  No 												

3. Active Suicidal Ideation with Any Methods (Not Plan) without Intent to Act Subject endorses thoughts of suicide and has thought of at least one method during the assessment period. This is different than a specific plan with time, place or method details worked out (e.g., thought of method to kill self but not a specific plan). Includes person who would say, "I thought about taking an overdose but I never made a specific plan as to when, where or how I would actually do it...and I would never go through with it." Have you been thinking about how you might do this?
 
If yes, describe:
		Yes  No 												

4. Active Suicidal Ideation with Some Intent to Act, without Specific Plan Active suicidal thoughts of killing oneself and subject reports having some intent to act on such thoughts, as opposed to "I have the thoughts but I definitely will not do anything about them." Have you had these thoughts and had some intention of acting on them?
 
If yes, describe:
		Yes  No 												

5. Active Suicidal Ideation with Specific Plan and Intent Thoughts of killing oneself with details of plan fully or partially worked out and subject has some intent to carry it out. Have you started to work out or worked out the details of how to kill yourself? Do you intend to carry out this plan?
 
If yes, describe:
		Yes  No 												
INTENSITY OF IDEATION														

The following features should be rated with respect to the most severe type of ideation (i.e., 1-5 from above, with 1 being the least severe and 5 being the most severe). Ask about time he/she was feeling the most suicidal.
		Most Severe												

Most Severe Ideation: _____
 
  
 Type # (1-5)	Description of Ideation	
   
 Frequency How many times have you had these thoughts?	(1) Less than once a week (2) Once a week (3) 2-5 times in week (4) Daily or almost daily (5) Many times each day	
 
 Duration When you have the thoughts, how long do they last?	(1) Fleeting - few seconds or minutes (4) 4-8 hours/most of day (2) Less than 1 hour/some of the time (5) More than 8 hours/persistent or continuous (3) 1-4 hours/a lot of time	
 
 Controllability Could/can you stop thinking about killing yourself or wanting to die if you want to?	(1) Easily able to control thoughts (4) Can control thoughts with a lot of difficulty (2) Can control thoughts with little difficulty (5) Unable to control thoughts (3) Can control thoughts with some difficulty (0) Does not attempt to control thoughts	
 
 Deterrents Are there things - anyone or anything (e.g., family, religion, pain of death) - that stopped you from wanting to die or acting on thoughts of committing suicide?	(1) Deterrents definitely stopped you from attempting suicide (4) Deterrents most likely did not stop you (2) Deterrents probably stopped you (5) Deterrents definitely did not stop you (3) Uncertain that deterrents stopped you (0) Does not apply	
 
 Reasons for Ideation What sort of reasons did you have for thinking about wanting to die or killing yourself? Was it to end the pain or stop the way you were feeling (in other words you couldn't go on living with this pain or how you were feeling) or was it to get attention, revenge or a reaction from others? Or both?	(1) Completely to get attention, revenge or a reaction from others (4) Mostly to end or stop the pain (you couldn't go on living with the pain or how you were feeling) (2) Mostly to get attention, revenge or a reaction from others (5) Completely to end or stop the pain (you couldn't go on living with the pain or how you were feeling) (3) Equally to get attention, revenge or a reaction from others (0) Does not apply	
  
		Type # (1-5)	Description of Ideation	Frequency How many times have you had these thoughts?	(1) Less than once a week (2) Once a week (3) 2-5 times in week (4) Daily or almost daily (5) Many times each day	Duration When you have the thoughts, how long do they last?	(1) Fleeting - few seconds or minutes (4) 4-8 hours/most of day (2) Less than 1 hour/some of the time (5) More than 8 hours/persistent or continuous (3) 1-4 hours/a lot of time	Controllability Could/can you stop thinking about killing yourself or wanting to die if you want to?	(1) Easily able to control thoughts (4) Can control thoughts with a lot of difficulty (2) Can control thoughts with little difficulty (5) Unable to control thoughts (3) Can control thoughts with some difficulty (0) Does not attempt to control thoughts	Deterrents Are there things - anyone or anything (e.g., family, religion, pain of death) - that stopped you from wanting to die or acting on thoughts of committing suicide?	(1) Deterrents definitely stopped you from attempting suicide (4) Deterrents most likely did not stop you (2) Deterrents probably stopped you (5) Deterrents definitely did not stop you (3) Uncertain that deterrents stopped you (0) Does not apply	Reasons for Ideation What sort of reasons did you have for thinking about wanting to die or killing yourself? Was it to end the pain or stop the way you were feeling (in other words you couldn't go on living with this pain or how you were feeling) or was it to get attention, revenge or a reaction from others? Or both?	(1) Completely to get attention, revenge or a reaction from others (4) Mostly to end or stop the pain (you couldn't go on living with the pain or how you were feeling) (2) Mostly to get attention, revenge or a reaction from others (5) Completely to end or stop the pain (you couldn't go on living with the pain or how you were feeling) (3) Equally to get attention, revenge or a reaction from others (0) Does not apply	
Type # (1-5)	Description of Ideation													
Frequency How many times have you had these thoughts?	(1) Less than once a week (2) Once a week (3) 2-5 times in week (4) Daily or almost daily (5) Many times each day													
Duration When you have the thoughts, how long do they last?	(1) Fleeting - few seconds or minutes (4) 4-8 hours/most of day (2) Less than 1 hour/some of the time (5) More than 8 hours/persistent or continuous (3) 1-4 hours/a lot of time													
Controllability Could/can you stop thinking about killing yourself or wanting to die if you want to?	(1) Easily able to control thoughts (4) Can control thoughts with a lot of difficulty (2) Can control thoughts with little difficulty (5) Unable to control thoughts (3) Can control thoughts with some difficulty (0) Does not attempt to control thoughts													
Deterrents Are there things - anyone or anything (e.g., family, religion, pain of death) - that stopped you from wanting to die or acting on thoughts of committing suicide?	(1) Deterrents definitely stopped you from attempting suicide (4) Deterrents most likely did not stop you (2) Deterrents probably stopped you (5) Deterrents definitely did not stop you (3) Uncertain that deterrents stopped you (0) Does not apply													
Reasons for Ideation What sort of reasons did you have for thinking about wanting to die or killing yourself? Was it to end the pain or stop the way you were feeling (in other words you couldn't go on living with this pain or how you were feeling) or was it to get attention, revenge or a reaction from others? Or both?	(1) Completely to get attention, revenge or a reaction from others (4) Mostly to end or stop the pain (you couldn't go on living with the pain or how you were feeling) (2) Mostly to get attention, revenge or a reaction from others (5) Completely to end or stop the pain (you couldn't go on living with the pain or how you were feeling) (3) Equally to get attention, revenge or a reaction from others (0) Does not apply													
<small>© 2008 Research Foundation for Mental Hygiene, Inc. C-SSRS—Baseline (Version 1/14/09) Page 1 of 2</small>														

SUICIDAL BEHAVIOR (Check all that apply, so long as these are separate events; must ask about all types)			
Actual Attempt: A potentially self-injurious act committed with at least some wish to die, as a result of act . Behavior was in part thought of as method to kill oneself. Intent does not have to be 100%. If there is any intent/desire to die associated with the act, then it can be considered an actual suicide attempt. There does not have to be any injury or harm , just the potential for injury or harm. If person pulls trigger while gun is in mouth but gun is broken so no injury results, this is considered an attempt. Inferring Intent: Even if an individual denies intent/wish to die, it may be inferred clinically from the behavior or circumstances. For example, a highly lethal act that is clearly not an accident so no other intent but suicide can be inferred (e.g., gunshot to head, jumping from window of a high floor/story). Also, if someone denies intent to die, but they thought that what they did could be lethal, intent may be inferred. Have you made a suicide attempt? Have you done anything to harm yourself? Have you done anything dangerous where you could have died? What did you do? Did you _____ as a way to end your life? Did you want to die (even a little) when you _____? Were you trying to end your life when you _____? Or did you think it was possible you could have died from _____? Or did you do it purely for other reasons /without ANY intention of killing yourself (like to relieve stress, feel better, get sympathy, or get something else to happen)? (Self-Injurious Behavior without suicidal intent) If yes, describe:			Lifetime Yes  No  Total # of Attempts <hr/>
Has subject engaged in Non-Suicidal Self-Injurious Behavior? (In) Interrupted Attempt: When the person is interrupted (by an outside circumstance) from starting the potentially self-injurious act (if not for that, actual attempt would have occurred). Overdose: Person has pills in hand but is stopped from ingesting. Once they ingest any pills, this becomes an attempt rather than an interrupted attempt. Shooting: Person has gun pointed toward self, gun is taken away by someone else, or is somehow prevented from pulling trigger. Once they pull the trigger, even if the gun fails to fire, it is an attempt. Jumping: Person is poised to jump, is grabbed and taken down from ledge. Hanging: Person has noose around neck but has not yet started to hang - is stopped from doing so. Has there been a time when you started to do something to end your life but someone or something stopped you before you actually did anything? If yes, describe:			Yes  No  Total # of interrupted <hr/>
Aborted Attempt: When person begins to take steps toward making a suicide attempt, but stops themselves before they actually have engaged in any self-destructive behavior. Examples are similar to interrupted attempts, except that the individual stops him/herself, instead of being stopped by something else. Has there been a time when you started to do something to try to end your life but you stopped yourself before you actually did anything? If yes, describe:			Yes  No  Total # of aborted <hr/>
Preparatory Acts or Behavior: Acts or preparation towards imminently making a suicide attempt. This can include anything beyond a verbalization or thought, such as assembling a specific method (e.g., buying pills, purchasing a gun) or preparing for one's death by suicide (e.g., giving things away, writing a suicide note). Have you taken any steps towards making a suicide attempt or preparing to kill yourself (such as collecting pills, getting a gun, giving valuables away or writing a suicide note)? If yes, describe:			Yes  No  Total # of <hr/>
Suicidal Behavior: Suicidal behavior was present during the assessment period?			Yes  No  Total # of <hr/>
Answer for Actual Attempts Only		Most Recent Attempt Date:  Enter Code	Most Lethal Attempt Date:  Enter Code
Actual Lethality/Medical Damage: 0. No physical damage or very minor physical damage (e.g., surface scratches). 1. Minor physical damage (e.g., lethargic speech; first-degree burns; mild bleeding; sprains). 2. Moderate physical damage; medical attention needed (e.g., conscious but sleepy, somewhat responsive; second-degree burns; bleeding of major vessel). 3. Moderately severe physical damage; medical hospitalization and likely intensive care required (e.g., comatose with reflexes intact; third-degree burns less than 20% of body; extensive blood loss but can recover; major fractures). 4. Severe physical damage; medical hospitalization with intensive care required (e.g., comatose without reflexes; third-degree burns over 20% of body; extensive blood loss with unstable vital signs; major damage to a vital area). 5. Death		Initial/First Attempt Date:  Enter Code	
Potential Lethality: Only Answer if Actual Lethality=0 Likely lethality of actual attempt if no medical damage (the following examples, while having no actual medical damage, had potential for very serious lethality: put gun in mouth and pulled the trigger but gun fails to fire so no medical damage; laying on train tracks with oncoming train but pulled away before run over).		Enter Code	Enter Code
0 = Behavior not likely to result in injury 1 = Behavior likely to result in injury but not likely to cause death 2 = Behavior likely to result in death despite available medical care			

